# **Dose and Dose Regimen**

The starting dose of 0.1 mg was based on both the Food and Drug Administration (FDA) guidance [7] and PK/PD modeling which predicted 20% BTK occupancy, which is considered to represent a minimum anticipated biological effect level.

Currently doses of 0.1, 0.5, 2.5, 4.4, 8.8, 17.5, 35, 70, and 105 mg have been tested in the SRD and 3.75, 5.75, 13 and 25 mg in the MRD and were shown to be safe and well tolerated. Draft PK data are summarized in Table 6.b and Table 6.c for the SRD and MRD, respectively.

Cohort (Dose)	C max (ng/mL)	T max * (hr)	AUC 24 (ng*h/mL)	AUC t (ng*h/mL)	$AUC_{\infty}$ (ng*h/mL)	Half-life (hr)

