# Table 6.c Summary of TAK-020 PK Parameters Cohorts 1 to 7 in MRD

Cohort (Dose)	C max (ng/mL)	T max * (hr)	AUC 24 (ng*h/mL)	AUC t (ng*h/mL)	AUC∞ (ng*h/mL)	Half-life (hr)	Accumulation Index

\*Median value.

Accumulation index=D9AUC24/D1AUC $\infty$ · TBD=to be determined.

Furthermore, plasma protein binding of TAK-020 in humans is higher than in the rat, (98.9% and 98.0% respectively) resulting in lower exposures to unbound (free) TAK-020 in humans at a given total exposure. Therefore unbound exposure estimates have been used to refine the dose escalation.

ТАК-020	
Study No. TAK-020-1001	Page 31 of 101
Protocol Incorporating Amendment No. 4.0	27 March 2017

The exposure at the maximum proposed dose would not exceed 1808 ng\*h/mL (total) and 19.9 ng\*h/mL (unbound) which is 2.19-fold unbound exposure at the LOAEL, and corresponds to a safety factor of 0.43.

As the PK  $t_{1/2z}$  for this compound remains short, PK washout would be expected within 24-hours and time dependency of PK could be evaluated without the need for any additional washout period following Day 1 in the MRD study Part 2. Further, due to the short  $t_{1/2z}$ , no accumulation in plasma PK is expected during the MRD. PD washout following Day 1 in MRD was not considered necessary for evaluation.

The following safety variables will be used to describe the safety and tolerability of TAK-020:

- Physical examination findings.
- TEAEs.
- Clinical laboratory test results.
- Vital sign measurements and weight.
- 12-lead ECGs.

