#### 8.1.3 Dose and Regimen

In Cohorts 1 to 9, doses of 0.1, 0.5, 2.5, 4.4, 8.8, 17.5, 35, 70, and 105 mg have been evaluated. The investigator or investigator's designee will instruct the subject on dosing procedures. All dosing will occur while subjects are in the clinic under the supervision of the PI or designee. On dosing days, subjects will be given TAK-020 or placebo oral solution. A separate pharmacy manual will describe how each dose regimen will be formulated.

Study drug will be administered at the same time on each dosing day (approximately 0800 hours). After initial administration, the dosing bottle shall be rinsed twice with about half the volume of the bottle with water. The rinse will be administered to the subject. The exact time of dose will be recorded in the source documents and on the appropriate eCRF.

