# 13.1.3.2 PK Parameters

Descriptive statistics [N, arithmetic mean, SD, median, minimum, maximum and percent coefficient of variation (%CV)] will be used to summarize the plasma PK parameters for TAK-020 by dose level and population. In addition, geometric mean and coefficient of variation will be computed for  $C_{max}$  and AUCs. All PK parameter data will be listed.

Power model will be used to assess dose proportionality for Cmax and AUC in each part.

The power model will be assumed as described by the following equation:

$$\log(PKParameter) = \beta_0 + \beta_1 \log(Dose) + \varepsilon$$

Where  $\beta_0$  is the intercept,  $\beta_1$  is the slope and  $\varepsilon$  is the random error.

The 90% confidence interval (CI) of the slope estimate will be presented. The dose proportionality would be declared when the 90% CI for  $\beta$ 1 lies entirely within the critical region:

$$\left(1 + \frac{\ln(0.80)}{\ln(r)}, 1 + \frac{\ln(1.25)}{\ln(r)}\right),$$

where r is the ratio of the highest and the lowest dose in this study. This criterion implies that the 90% CI for the ratio of the central values of PK parameter of interest from the highest dose to the lowest dose is contained completely within the bioequivalence range of (0.80, 1.25).

Analysis of variance (ANOVA) will be performed for  $T_{max}$  and  $\lambda_z$  after a single or multiple dose administration to evaluate the effect of dose on  $T_{max}$  for SRD and MRD parts and  $\lambda_z$  for SRD part.

ANOVA will be used to assess time dependency for Part 2 (MRD). The natural log-transformed AUCs and  $C_{max}$  will be used as response variable and dose level, Day and the interaction of dose level and Day will be fixed factors. Within the frame work of ANOVA, 90% CIs for the ratio of AUCs and  $C_{max}$  central values between Days 9 and 1 will be presented.

Detailed analysis methodologies will be presented in SAP as necessary.

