# 6.0 DETERMINATION OF SAMPLE SIZE

The sample sizes chosen of 8 subjects per cohort (6 active: 2 placebo) in Part 1 and 2 is considered to be sufficient for evaluation of safety, tolerability, PK and the PD of TAK-020 in each cohort. The sample size was not based on statistical power considerations.

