CL R	Renal clearance, calculated as Ae 0-24 /AUC 24 .

Specific or additional PK parameters may be added as appropriate per the Clinical Pharmacology Analysis Plan (CPAP).

PK parameters of TAK-020 will be summarized by treatment using descriptive statistics. In addition, geometric mean and coefficient of variation will be computed for  $C_{max}$  and AUCs. PK

TAK-020-1001	Page 18 of 31
Statistical Analysis Plan Final	22 May 2017

parameters will be summarized separately for the SRD and MRD portions of the study. Individual PK parameters will be listed.

Dose proportionality will be tested for  $C_{max}$  and AUCs of both SRD and MRD using a power model. The power fit will be assumed as described by the following equation:

 $\ln(PK \ Parameter) = \beta_0 + \beta_1 \ln(Dose) + \varepsilon$ 

where  $\beta_0$  is the intercept,  $\beta_1$  is the slope and  $\varepsilon$  is the random error. The 90% CI for  $\beta_1$  will be presented and dose proportionality would be declared when this CI lies entirely within the critical region  $\left(1 + \frac{\ln(0.80)}{\ln(r)}, 1 + \frac{\ln(1.25)}{\ln(r)}\right)$ , where *r* is the ratio of the highest and lowest dose in the study. This criterion implies that the 90% CI for the ratio of the central values of the PK parameter of interest from the highest dose to the lowest dose is contained completely within the bioequivalence range of (0.80, 1.25) [2].

For SRD, the effect of dose on Tmax and  $\lambda z$  will be evaluated using analysis of variance (ANOVA) with treatment as a fixed effect. Means and standard deviations will be presented for all treatments along with a p-value of overall treatment effect. A similar analysis will be completed for Tmax within the MRD portion of the study. This analysis will be done separately for Day 1 and Day 9.

ANOVA will be used to assess time dependency for Part 2 (MRD). The natural log-transformed AUCs and Cmax will be used as response variable and dose level, Day and the interaction of dose level and Day will be fixed factors. Within the frame work of ANOVA, 90% CIs for the ratio of AUCs and Cmax central values between Day 9 and Day 1 will be presented.

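### The dose effect on lambda-z in Part 1 is tested only by an unordered ANOVA p-value; adding the log-log slope with a 90% CI already planned for Cmax and AUC would be a cheap improvement

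*SAP*

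**What the plan says.** SAP 7.9.1 states that in the single-dose part the effect of dose on Tmax and lambda-z "will be evaluated using analysis of variance (ANOVA) with treatment as a fixed effect". The output is then fixed: "Means and standard deviations will be presented for all treatments along with a p-value of overall treatment effect". Protocol 13.1.3.2 plans an ANOVA "after a single or multiple dose administration to evaluate the effect of dose on" Tmax in both parts and lambda-z in the single-dose part only. Neither document adds a trend test, contrast, confidence interval, margin, significance level or decision rule for lambda-z or half-life.

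The neighbouring analyses in SAP 7.9.1 are specified differently. Just before this, Cmax and AUCs are regressed on dose on the natural-log scale, with a 90% CI for the slope and a pre-set region for declaring proportionality. Just after it, the Day 9 to Day 1 ratios of Cmax and AUCs get 90% CIs. All PK parameters, including lambda-z and half-life, are also summarised descriptively by treatment and listed.

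Half-life is a secondary endpoint (Protocol 5.2.2, SAP 5.2) and equals ln(2)/lambda-z (SAP Table 7.c).

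**The concern.** The nine groups are doses in a known order, but the ANOVA treats them as unordered labels. It spreads its sensitivity over 8 numerator degrees of freedom, when the natural question (does elimination slow or speed up as dose rises?) needs one. Its single p-value also says nothing about the size of any change. If it is not significant, the specified inference puts no bound on how far half-life could have moved between the lowest and highest dose.

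At stake is how well a secondary PK conclusion is supported. The primary safety objective is not involved.

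**Working it through.** The plan gives no power figure for this analysis, so there is none to reproduce. SAP 6.0 says: "The sample size was not based on statistical power considerations".

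**Inputs from the documents**
- Doses: "Currently doses of 0.1, 0.5, 2.5, 4.4, 8.8, 17.5, 35, 70, and 105 mg have been tested in the SRD" (Protocol 6.2). So r = 105/0.1 = 1050 and ln r = 6.957.
- Subjects: "The sample sizes chosen of 8 subjects per cohort (6 active: 2 placebo) in Part 1 and 2" (SAP 6.0). Placebo subjects are left out of the PK summaries, so 9 × 6 = 54 contribute.
- ANOVA degrees of freedom: 8 and 45. Slope degrees of freedom: 1 and 52.

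**Assumptions, because the documents available show no value**
- Two-sided 5% level.
- Between-subject CV of lambda-z from 20% to 50%, log-normal, so σ² = ln(1 + CV²).
- A 1.5-fold total change in half-life, linear in ln(dose).
- Lambda-z estimable in all 54 subjects.

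**Formulas.** The size of the slope is b1 = ln 1.5 / ln 1050 = 0.4055/6.957 = 0.0583. The spread of ln(dose) is Sxx = 6 × 42.37 = 254.2. For a log-linear trend both tests have the same noncentrality, b1² × Sxx / σ² = 0.864/σ². They differ only in the degrees of freedom over which it is spread. The slope's 90% CI for the highest-to-lowest ratio is the estimate multiplied or divided by exp(t × σ/√Sxx × ln 1050), where t is the 95th percentile on 52 df.

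| CV | σ² | noncentrality | ANOVA misses, ln scale | ANOVA misses, untransformed | slope misses | 90% CI factor |
|---|---|---|---|---|---|---|
| 20% | 0.039 | 22.0 | 10.8% | 10.7% | 0.4% | 1.16 |
| 30% | 0.086 | 10.0 | 49.4% | 49.7% | 12.6% | 1.24 |
| 40% | 0.148 | 5.82 | 70.7% | 71.9% | 34.2% | 1.32 |
| 50% | 0.223 | 3.87 | 80.2% | 81.8% | 51.2% | 1.41 |

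The ln-scale ANOVA and slope columns come from the noncentral F. The SAP mentions no transformation of lambda-z, so the untransformed column was simulated (100,000 trials per row, half-life rising with dose). If half-life falls with dose, the untransformed ANOVA misses 13.5%, 55.3%, 75.8% and 84.3%.

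**Sensitivity at 40% CV**
- *Level.* At a two-sided 10% level, which matches a 90% CI, the misses are 58% (ANOVA, ln scale) and 23% (slope).
- *Fewer evaluable subjects.* With 5 or 4 per dose, the ln-scale ANOVA misses 76% or 82%.
- *No lambda-z at 0.1 and 0.5 mg.* Seven doses remain, r = 105/2.5 = 42, and Sxx falls to 70.65, or 28% of its full value. The same slope is now only a 42^0.0583 = 1.24-fold change over the remaining range. Noncentrality is 0.0034 × 70.65/0.148 = 1.62. Power falls to about 11% (ANOVA, ln scale) and 24% (slope).

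**A different shape.** If a 1.5-fold change occurs at the top dose only, at 30% CV, power is 51% for the ln-scale ANOVA, 36% for the untransformed ANOVA and 25% for the slope. If it occurs at the top two doses, the ln-scale ANOVA has 80% and the slope 68%.

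**The case against.** Much of the case on the other side stands.

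- **A reader might infer that the plan will treat p > 0.05 as proof of no dose effect.** Neither document says so, and nothing is gated on this p-value. Means and SDs by dose are part of the same output, and by-dose summaries and listings are also planned, so a visible trend would not be hidden. What is missing is an interval for the change across doses.
- **A reader might infer that the case for washout and no accumulation depends on this test.** Protocol 6.2 does say that "no accumulation in plasma PK is expected during the MRD" because half-life is short. That is design reasoning set beside draft PK data, not a conclusion awaiting this ANOVA. Part 2 assesses the matter directly, through accumulation ratios and Day 9 to Day 1 ratios with 90% CIs. Nor is a 1.5-fold change shown to matter there. With the animal half-lives in Protocol 4.1 purely as illustration, the once-daily factor 1/(1 − 2^(−24/t)) moves from 1.01 to 1.06 (3.8 to 5.7 h) or from 1.11 to 1.28 (7.3 to 10.95 h).
- **Clearance is largely covered already.** CL/F after a single dose is Dose/AUC∞, and AUCs get the power model. A clearance-driven slowing should show there; a volume-driven change in half-life might not.
- **The slope's gain can be overstated.** Protocol 6.1 provides for cohorts in which exposure is seen in fewer than 4 active subjects, and the lowest doses carry much of the slope's information.
- **The slope is not better for every pattern.** It loses to the ANOVA when only the top dose changes, and to the ln-scale ANOVA when the top two change.

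These points lower the importance of the matter and rule out replacing the ANOVA. They do not supply the missing estimate and interval.

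**Conclusion.** The point holds as an optional improvement. The formal assessment of dose-dependent elimination in Part 1 is an unordered test with no estimate or interval, while the same SAP section gives Cmax and AUCs a slope with a 90% CI. For a gradual 1.5-fold change, the ANOVA misses about 11% to 82% of the time over CVs of 20% to 50%, against about 0.4% to 51% for the slope.

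No single miss rate should be quoted alone. The 72% figure, for instance, applies only at an assumed 40% CV. All the rates rest on an assumed CV, effect size, level, log-linear shape and full evaluability. The by-dose summaries, the AUC power model and the Part 2 accumulation and Day 9 to Day 1 analyses are unaffected.

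**What to change.** In SAP 7.9.1:

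1. Add lambda-z to the power model for the single-dose part: ln(lambda-z) = b0 + b1 × ln(Dose). Report b1 and the implied highest-to-lowest half-life ratio, r^(−b1), each with a 90% CI. Fit over the doses where lambda-z can be estimated, take r from those doses, and report how many subjects contribute at each.
2. Keep the ANOVA, run on ln(lambda-z), with equal standing beside the slope, because it is more sensitive to a change confined to the top doses.
3. State that a non-significant ANOVA p-value alone will not be reported as dose-independent elimination.

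The cost is a few sentences in the SAP and one more model using code already needed for Cmax and AUCs, with no new data. The downside is that the slope assumes a monotone log-linear trend, which is why the ANOVA stays.

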TAK-020 is poorly soluble, but using a Captisol formulation, appears well-absorbed across nonclinical species, with the predicted fraction absorbed in humans estimated as 98% from oral dosing solution. In nonclinical studies, TAK-020 was absorbed rapidly and extensively after oral administration, with peak plasma concentrations generally occurring within 2 hours postdose. Terminal disposition phase half-life ( $t_{1/2z}$ ) of TAK-020 after oral administration was 4.4-7.3 hours in rats and 3.8-6.7 hours in dogs. The oral bioavailability (BA) of TAK-020 in animals was low (12.6%-21.8% in rats and 8.17% to16.5% in dogs). Absorption could be modulated by P-glycoprotein (P-gp), since TAK-020 is likely to be a P-gp substrate based on results obtained from a study using LLC-PK1-MDR1 cells.

TAK-020 is mainly metabolized by CYP3A4, CYP2C19, and CYP1A2, and is also metabolized to a minor extent by CYP2D6, CYP2C8, and CYP2C9 (TAK-020-10222, TAK-020-10223). TAK-020 has inhibitory effects on CYP2C19 activity with 50% inhibitory concentration (IC50) of 10  $\mu$ mol/L without preincubation and 6.3  $\mu$ mol/L with pre-incubation (TAK-020-10133). TAK-020 has little or no time-dependent inhibitory effects on the other cytochrome P-450 (CYP) activities (CYP1A2, CYP2B6, CYP2C8, CYP2C9, CYP2D6, or CYP3A4/5) up to 30  $\mu$ mol/L

TAK-020	
Study No. TAK-020-1001	Page 22 of 101
Protocol Incorporating Amendment No. 4.0	27 March 2017

(TAK-020-10133). TAK-020 is a weak inducer for CYP1A2 and CYP3A4 (TAK-020-10134). TAK-020 was found to be an inducer for CYP2B6.

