(g) Clinical laboratory tests (hematology, serum chemistries, and urinalysis) will be collected at Screening, Day -1, Days 2, 3, 5, 8 and prior to check-out (Day 10) or Early Termination. Laboratory samples will be taken following a minimum 10-hour overnight fast

(h) Pregnancy test (hCG) will be performed for all female subjects.

(i) Triplicate 12-lead ECGs printed in standard format, will be collected at Screening, Check-in (Day -1), Day 1 predose (0 hours) and at 1, 4, 12, and 24 hours postdose, Days 3, 5, 9, 10 at predose (0 hours) or Early Termination. For ad hoc ECGs, as required, see Section 9.1.11.

(j) Telemetry will be performed approximately 2 hours predose until 12 hours postdose on Days 1 and 9 only. Ten (10) sec triplicate ECGs will be extracted at PK time-points for manual reading and precise ECG reading including QT interval measurement.

(k) One blood sample (6 mL) will be collected prior to dosing on Day 1.

(I) Two whole blood samples (2.5 mL per sample) will be collected at predose on Days 1, 3 and 9.

(m) Blood samples for PK analysis will be collected at predose on Day 1 (within 30 minutes prior to dosing) and at 0.25, 0.5, 0.75, 1, 2, 3, 4, 6, 8, 10, 12, 16, 24, 36, and 48 hours postdose and at predose on Day 9 (within 30 minutes prior to dosing) and at 0.25, 0.5, 0.75, 1, 2, 3, 4, 6, 8, 10, 12, 16, and 24 hours postdose.

(n) Urine samples for PK analysis will be collected on Day 1 and Day 9 at predose (-12-0), and 0-6, 6-12, 12-24 hour postdose intervals

(r) PTEs will be collected from signing of informed consent up until dosing on Day 1

(s) Hematology and Serum Chemistry only.

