The first cohort for the MRD will receive a dose of 3.75 mg, with a predicted exposure at steady state estimated to be below the no observed adverse effect level (NOAEL) rate (63 ng\*h/mL). The predicted steady state exposure in the first MRD cohort will be approximately 10-fold lower than the highest predicted steady state exposure determined from the SRD data. The MRD will comprise a maximum of 7 cohorts, each cohort with 8 subjects randomized with 6 receiving TAK-020 and 2 receiving placebo. In each successive cohort after the first, the dose increments will increase the predicted exposures by no more than 2-fold. The predicted steady state exposure in the MRD will not exceed the maximum exposure observed in the SRD.

A schematic of the study design is included as Table 4.a. A schedule of assessments is listed in Appendix A.

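### The Part 2 Day 9/Day 1 ANOVA names no subject term although each subject contributes both days; run as written, its 90% confidence intervals are too wide

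*SAP*

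**What the plan says.** SAP 7.9.1 (Pharmacokinetic Analysis) models natural-log AUCs and Cmax from Part 2 by ANOVA: "dose level, Day and the interaction of dose level and Day will be fixed factors". From that model, "90% CIs for the ratio of AUCs and Cmax central values between Day 9 and Day 1 will be presented". Protocol 13.1.3.2 lists the same three terms, as does the statistical part of the Protocol 2.0 summary. Protocol 13.1.3.2 also says "Detailed analysis methodologies will be presented in SAP as necessary", but the SAP repeats the model without adding to it. SAP 7.9.1 mentions a Clinical Pharmacology Analysis Plan only as a source of specific or additional PK parameters, not of this model.

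On the design, Protocol Appendix A (Part 2, footnote m) schedules serial sampling from Day 1 predose to "48 hours postdose and at predose on Day 9 (within 30 minutes prior to dosing") and on to 24 hours after the Day 9 dose, in the same subjects. SAP 4.4 plans "a maximum of 7 cohorts, each cohort with 8 subjects randomized with 6 receiving TAK-020". Protocol 6.2 names four MRD dose levels already tested: 3.75, 5.75, 13 and 25 mg.

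For Tmax in the MRD part, SAP 7.9.1 takes another route: "This analysis will be done separately for Day 1 and Day 9".

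**The concern.** The two observations from one subject share that subject's clearance and bioavailability, so they are expected to be positively correlated. A model with only dose level, Day and their interaction treats them as independent. The residual then holds between-subject plus within-subject variance, although between-subject variance cancels out of the Day 9 minus Day 1 difference. The Tmax analysis escapes this because it never puts both days in one model.

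This is the only planned inferential comparison of Day 9 with Day 1; the accumulation ratios R and Rac(AUC) are only summarised and listed. The question is not idle. Protocol 4.1 states that "TAK-020 is a weak inducer for CYP1A2 and CYP3A4" and names both enzymes among the main metabolic routes, so a modest fall in exposure on repeat dosing is plausible. Protocol 6.2 relies on Part 2 for the answer, saying "time dependency of PK could be evaluated without the need for any additional washout period following Day 1". An over-wide interval is what would hide such a fall.

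**Working it through.** The plan gives no variance, interval width or power for this analysis, so there is no figure of its own to reproduce.

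**Inputs from the documents.** n = 6 active subjects per cohort; k = 7 cohorts at most, or k = 4 (the dose levels named in Protocol 6.2); 90% two-sided interval; natural-log scale; two days per subject.

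**Assumptions.** Between-subject CV 40% and within-subject CV 20%, varied below. On the log scale, σb² = ln(1 + 0.40²) = 0.1484 and σw² = ln(1 + 0.20²) = 0.0392. The total is σT² = 0.1876, and the Day 1-Day 9 correlation is ρ = 0.1484/0.1876 = 0.79.

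**Half-widths for one dose level (log scale).**

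- As written: t(0.95; 2k(n−1)) × √(2σT²/n), with 40 df (k = 4) or 70 df (k = 7).
- With a subject term: t(0.95; k(n−1)) × √(2σw²/n), with 20 or 35 df.

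For an interval pooled over dose levels, replace n under the root by nk.

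**Width ratio.** [t(2k(n−1)) / t(k(n−1))] / √(1−ρ), where 1/√(1−ρ) = √(0.1876/0.0392) = 2.19.

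- k = 4: (1.6839/1.7247) × 2.19 = 2.14.
- k = 7: (1.6669/1.6896) × 2.19 = 2.16.

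Doubling the error df takes back only 2.4% (k = 4) or 1.3% (k = 7) of the width. The as-written interval is the wider one whenever ρ exceeds 1 − (t ratio)², which is 0.047 (k = 4) or 0.027 (k = 7).

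**Dependence on ρ alone.**

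| ρ | k = 4 | k = 7 |
|---|---|---|
| 0.3 | 1.17 | 1.18 |
| 0.5 | 1.38 | 1.40 |
| 0.7 | 1.78 | 1.80 |
| 0.8 | 2.18 | 2.21 |
| 0.9 | 3.09 | 3.12 |

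**Simulation at CVs 40%/20%.** Trials were generated with a log-normal subject effect plus residual, 40,000 per setting. Median half-widths are multiplicative. The last two columns give the chance that the whole 90% CI lies below 1 when the true ratio is 0.80.

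| Interval | Half-width, as written | Half-width, subject term | Below 1, as written | Below 1, subject term |
|---|---|---|---|---|
| Per dose | ×/÷1.51 | ×/÷1.21 | about 6% | about 60% |
| Pooled, 4 cohorts | ×/÷1.23 | ×/÷1.10 | 59% | 98% |
| Pooled, 7 cohorts | ×/÷1.17 | ×/÷1.08 | 92-93% | 100% |

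Coverage is about 99.9% as written and 90% with the subject term. At a true ratio of 0.70 the per-dose chances are 32% and 91-92%; pooled, they are 99-100% and 100%.

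**Range.** Over between-subject CV 30-50% and within-subject CV 20-30%, the width ratio runs from 1.38 (30%/30%, k = 4, ρ = 0.5) to 2.55 (50%/20%, k = 7), with coverage 98-100%. At a true ratio of 0.80 the chances of a CI below 1, as written against with the subject term, are:

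- per dose: 2-17% against 35-61%;
- pooled over 4 cohorts: 31-80% against 81-98%;
- pooled over 7 cohorts: 63-98% against 96-100%.

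Fitting both models to one balanced simulated data set gave the same point estimate (−0.2308 on the log scale), so only the standard error differs.

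**The case against.** The sentence lists fixed factors. A random subject effect is not one, so an analyst could add it without contradicting the text. That is true, and the defect is one of omission. But the SAP is where the error structure should be fixed, and two programmers could both follow it and report intervals differing about twofold.

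The size rests on assumed CVs, because the PK values in Protocol Tables 6.b and 6.c are not visible. At ρ = 0.3 the excess width is only 17-18%, and a negative correlation would reverse the direction. This stands as a limit on the magnitude. The direction needs only ρ above about 0.05, which repeat AUC or Cmax in the same person should exceed.

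The plan attaches no acceptance range to these intervals, the sample size was not based on power, and the chance of a CI below 1 is not a planned criterion. All of that stands; those probabilities serve only to show what the extra width means. Readers will also see R and Rac(AUC), with their spread and the individual values, and could form a paired interval themselves. That softens the loss but does not correct the interval reported as 90%.

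Finally, too wide is conservative. It is so against a false signal, but not against missing a real fall in exposure.

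**Conclusion.** The concern holds. The documents describe a within-subject comparison and list a model without a subject term. For any within-subject correlation above about 0.05, the intervals from that model are too wide and their stated 90% level is wrong. At the assumed 40%/20% CVs the excess is 2.1- to 2.2-fold; across the CV range examined it is 1.4- to 2.6-fold, and less if the correlation is below 0.5. The loss is large for per-dose intervals or few cohorts, and small for an interval pooled over 7 cohorts at the central CVs. The SAP does not say which of these is meant.

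The harm is lost precision and a mislabelled confidence level in a secondary PK analysis. The primary safety endpoints are untouched, no declaration depends on these intervals, and the point estimate is unchanged with complete data. If a subject lacks Day 9, the as-written contrast also becomes partly a between-subject one. This should be fixed before the analysis is run.

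**What to change.** In SAP 7.9.1, add subject nested within dose level as a random effect, or an equivalent two-by-two within-subject covariance, to the model on the log parameters. State that the Day 9/Day 1 90% CIs come from that model.

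The SAP change is sufficient to settle the analysis, because Protocol 13.1.3.2 defers detailed methods to the SAP and its list of fixed factors does not conflict with a random effect. The protocol wording should be brought into line when it is next amended.

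Two optional clarifications fit in the same edit: whether the intervals are per dose level, pooled, or both; and which AUC forms the ratio, for example AUCτ on Day 9 over AUC∞ on Day 1, which the SAP already defines as R.

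The cost is one model term and a sentence or two of text. No new data, samples or subjects are needed.
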